9.5.1.4. Vital Signs

Descriptive statistics will be provided for the vital sign measurements by scheduled time of evaluation, as well as for the change from baseline. The baseline value is defined as the last non-missing value before the initial administration of study treatment. A listing of vital signs data will be generated.

9.5.1.5. Other

Listings of all other safety endpoints (e.g., physical examination findings) will be generated.

9.5.2. Pharmacokinetics Analysis

Pharmacokinetic analysis and statistical analysis of PK endpoints will be conducted in accordance with the protocol, SAP, and the Daiichi Sankyo Non-Compartmental Analysis Guidelines.

9.5.2.1. Pharmacokinetic Parameters

Pharmacokinetic and statistical analysis will be performed using appropriate software; e.g., Phoenix™ WinNonlin® (Version 8.0 or higher, Certara, L.P.) and/or SAS® (Version 9.4 or higher, SAS Institute Inc.). Pharmacokinetic analysis will be performed using a non-compartmental analysis approach.

The following PK parameters will be calculated for plasma and whole blood quizartinib, plasma and whole blood AC886, plasma ^{14}C -quizartinib, plasma ^{14}C -AC886 and plasma total radioactivity, as applicable.

Cmax	The maximum observed concentration
Tmax	Time to reach maximum observed concentration
Kel	First order rate constant associated with the terminal portion of the concentration-time curve. This is estimated via linear regression of time vs log concentration.
t _{1/2}	Terminal half-life
AUClast	AUC from the time of dosing to time Tlast
AUCinf	AUC from the time of dosing extrapolated to infinity
AUCextr (%)	Percentage of AUCinf that is due to extrapolation from Tlast to infinity Note: If AUCextr is greater than 20%, AUCinf and related parameters (CL/F and Vz/F) for the specific treatment will be summarized with and without subjects for whom AUCextr >20%.
Clast	The last observed concentration
Tlast	Time of the last measurable (non-zero) concentration

CL	Total body clearance following single-dose iv administration (for plasma ¹⁴ C-quizartinib only)
CL/F	Apparent total body clearance following single-dose extravascular administration (for plasma and whole blood quizartinib only)
Vz	Volume of distribution based on the terminal phase following a single-dose of iv administration (for plasma ¹⁴ C-quizartinib only)
Vz/F	Apparent volume of distribution based on the terminal phase following a single-dose of extravascular administration (for plasma and whole blood quizartinib only)
MPR Cmax	Metabolite-to-parent ratio for Cmax (for plasma and whole blood AC886 and plasma ¹⁴ C-AC886 only)
MPR AUClast	Metabolite-to-parent ratio for AUClast (for plasma and whole blood AC886 and plasma ¹⁴ C-AC886 only)
MPR AUCinf	Metabolite-to-parent ratio for AUCinf (for plasma and whole blood AC886 and plasma ¹⁴ C-AC886 only)
F	The fraction of the administered dose systemically available
Kbp	Whole blood-to-plasma concentration ratio

The following PK parameters will be calculated for total radioactivity quizartinib and AC886 in urine and feces by discrete collection interval and cumulatively as applicable.

Ae(t1-t2)	Amount of total radioactivity, quizartinib and AC886 excreted in urine/feces from time t1 to time t2 for each collection interval
Fe(t1-t2)	Amount of total radioactivity, quizartinib and AC886 excreted in urine/feces expressed as a percentage of the IV (total radioactivity) or oral (quizartinib and AC886) dose administered from time t1 to time t2 for each collection interval

9.5.2.2. Statistical Analysis of Pharmacokinetic Endpoints

The PK Analysis Population and the PK Evaluable Population will be used for PK analyses, details of which will be presented in the SAP.

Using the PK Analysis Population, descriptive statistics will be presented for plasma and whole blood concentrations at each sampling time point. Plasma concentration-time data will be analyzed using non-compartmental methods. Whole blood-to-plasma quizartinib and AC886 concentration ratios (Kbp) will also be calculated at each sampling time point.

The PK Evaluable Population will be used for the calculation and summaries of the PK parameters listed in Section 9.5.2.1.

Note that when percent extrapolated AUC (AUCextr (%)) is greater than 20%, AUCinf and related parameters will be summarized with and without those individuals having >20% AUCextr (%). For the primary analysis, including calculation of absolute bioavailability (F), individuals having >20% AUCextr (%) will be excluded. An additional subset may be required in order to include individuals having >20% AUCextr (%); this will be documented in the clinical study report.

Absolute bioavailability (F) will be calculated based on the dose-normalized quizartinib plasma AUC_{inf} after the oral dose (data from the cold assay [i.e., ¹²C-quizartinib] will be used for this analysis) to the dose-normalized AUC_{inf} after the IV dose (data from the hot assay [i.e., ¹⁴C-quizartinib] will be used for this analysis).

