3. OBJECTIVES, OUTCOME MEASURES, AND ENDPOINTS

3.1. Primary Objective/Endpoints

The primary objective of this study is:

- To determine the absolute oral bioavailability of quizartinib.

The primary endpoints of this study are:

- Absolute bioavailability assessment based on the PK parameters AUClast and AUCinf for quizartinib following IV and oral administrations.

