4. STUDY DESIGN

4.1. Overall Design

This is a single center, open-label, Phase 1 study to determine the absolute oral bioavailability in healthy male subjects. It is planned to enroll 8 subjects to ensure data in a minimum of 6 subjects who are evaluable for PK. An evaluable subject is defined as a subject who has received both the oral and IV microtracer IMPs (i.e., a single, oral dose of 60 mg quizartinib dihydrochloride tablets [2 x 30 mg tablets] and an IV administration of 50 μ g ^{14}C -quizartinib solution for infusion 10 μ g/mL containing NMT 22.84 kBq ^{14}C in 5 mL [NMT 4.6 kBq/mL] over 15 minutes at 4 hours post-oral dose) and has sufficient samples for evaluation of plasma PK parameters.

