5.4. Screening Failures, Re-screening, and Subject Replacement

This study permits the re-screening of a subject who has discontinued the study as a pre-treatment failure (ie subject has not been treated); the reason for failure must be temporary and expected to resolve. If re-screened, the subject must be re consented.

Subjects who withdraw or are withdrawn from the study will not be replaced.

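### Does leaving subjects with more than 20% extrapolated AUC out of the primary bioavailability analysis waste data and undermine the target of 6 subjects?

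*Combined protocol and SAP*

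**What the plan says.** Section 9.5.2.2 sets the rule: "For the primary analysis, including calculation of absolute bioavailability (F), individuals having >20% AUCextr (%) will be excluded". The same paragraph says that "AUCinf and related parameters will be summarized with and without those individuals having >20% AUCextr" and adds: "An additional subset may be required in order to include individuals having >20% AUCextr (%); this will be documented in the clinical study report". The note to AUCextr in Section 9.5.2.1 is tied to route: AUCinf, CL/F and Vz/F "for the specific treatment will be summarized with and without subjects for whom AUCextr >20" percent. F is the ratio of dose-normalized AUCinf, unlabeled quizartinib over 14C-quizartinib (Section 9.5.2.2). The primary endpoint in Section 3.1 is "Absolute bioavailability assessment based on the PK parameters AUClast and AUCinf for quizartinib following IV and oral administrations".

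On numbers, Section 4.1 says "It is planned to enroll 8 subjects to ensure data in a minimum of 6 subjects who are evaluable for PK". Section 9.2 words this as a target of at least 6, allows for the loss of up to 2 dosed subjects, and states that the number was not derived from power. Section 5.4 adds "Subjects who withdraw or are withdrawn from the study will not be replaced". Section 9.1 says that no hypothesis is tested. To be evaluable (Sections 4.1 and 9.4.1), a subject needs both doses and enough samples; extrapolation is not mentioned.

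**The concern.** Two features look wrong together.

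- **An extra loss.** The sample size allows 2 losses from 8 under a definition without an extrapolation limit. The primary analysis then applies such a limit, and withdrawn subjects are not replaced. Six evaluable subjects need not mean six values of F.
- **A rule that seems misplaced.** A 20% limit makes sense for a stand-alone AUCinf or clearance. Here both curves are measured in the same subject over the same days and should share a terminal slope. If an error in the tail inflates numerator and denominator alike, it drops out of the ratio, and excluding the subject gains little.

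If both points held, the primary estimate could rest on fewer than 6 subjects, chosen by the shape of their own profiles, while the result in all evaluable subjects remained optional.

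**Working it through.** **Inputs.** 8 enrolled and up to 2 lost (Section 9.2). Quizartinib half-life about 73 h, AC886 about 119 h, last sample at 504 h (Section 4.2). Infusion starts at 4 h, so the last sample is 500 h after the IV dose (Table 1.1). Different assays serve the two routes: AMS for 14C drug, HPLC MS/MS for unlabeled drug (Section 4.2). The documents give neither quantification limits nor the variability of half-life; values for these are assumptions.

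**1. The plan's own figure.** 8 - 2 = 6. This is an allowance, not a power calculation.

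**2. Expected extrapolation.** For a mono-exponential decline, the extrapolated share is x = 2^(-Tlast/t1/2).

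- Oral: 2^(-504/73) = 0.83%. IV: 2^(-500/73) = 0.87%.
- Even with a half-life of 119 h: 5.3% and 5.4%.

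**3. What would trigger the rule.** Setting x = 20% gives Tlast = t1/2 × log2(5).

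- At 73 h: 73 × 2.322 = 169.5 h. A 14C curve last measurable at the 144 h draw (140 h after the infusion starts) has 26.5% extrapolated; at the 192 h draw (188 h) it has 16.8%. So 14C drug must become unmeasurable before the 192 h draw.
- With data to the end: t1/2 = 500/2.322 = 215 h (IV) or 504/2.322 = 217 h (oral), about three times the stated value.

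**4. How often a long half-life would do it.** Assume a log-normal half-life with geometric mean 73 h and both curves measurable to the end.

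| Assumed CV | P(half-life > 215 h) | P(at least 6 of 8 kept) | P(all 6 kept, allowance already used) |
|---|---|---|---|
| 30% | 0.01% | >0.999 | 0.999 |
| 50% | 1.1% | >0.999 | 0.936 |
| 70% | 4.3% | 0.996 | 0.766 |

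Binomial chances of fewer than 6 remaining, 4%, 20% and 45% at a loss of 10%, 20% and 30% per subject, are correct arithmetic (0.038, 0.203, 0.448). They describe loss for any reason, including the withdrawals already allowed for, and so do not measure what this rule adds.

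**5. Does the error cancel?** With a relative error e in the terminal slope, the estimated AUCinf divided by the true value is (1 - x) + x/(1 + e). The error in F is the oral value over the IV value, minus 1.

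| Oral Tlast | IV Tlast | Slope error, oral / IV | Error in F |
|---|---|---|---|
| 144 h | 140 h | -20% / -20% | -0.2% |
| 504 h | 140 h | -20% / -20% | -6.0% |
| 504 h | 92 h | -20% / -20% | -9.3% |
| 144 h | 140 h | +20% / -20% | -10.2% |

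Second row in full: oral 1 + 0.0083 × 0.25 = 1.0021; IV 1 + 0.2647 × 0.25 = 1.0662; ratio 0.940.

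Cancellation needs two conditions: similar extrapolated shares and the same slope error. The first fails when the 14C curve ends early beside a complete oral curve, because there is almost no oral tail to offset the IV tail. The second is not assured, because the two curves come from different assays. When a long half-life triggers the rule, both curves run to the end and the shares are alike, so a shared error would cancel. Step 4 shows that this case should be rare.

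**The case for a change.** The strongest argument for keeping these subjects is precision. One subject whose F is off by 6.2% (error on the IV slope only, IV curve ending at 140 h) moves a mean of 8 by 6.2/8 = 0.8%; an error of 10.2% moves it by 1.3%. At an assumed 20% CV of F, the 95% half-width, t × 0.20/√n, rises from 16.7% with 8 subjects to 21.0% with 6. AUClast does not rescue such a subject: with ends at 504 h and 140 h, its ratio overstates F by (1 - 0.0083)/(1 - 0.2647) - 1 = 35%.

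This shows that making the full set primary would also be defensible. It does not show that the plan is wrong. The 20% slope error is assumed; at -40% on IV alone, the IV AUCinf is too high by 0.2647 × (1/0.6 - 1) = 17.6% and F is off by about -15%. Dividing by 8 supposes one affected subject. If the assay cut several 14C curves short and their errors had the same sign, the bias would remain in the mean.

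Some points of wording stand. The exclusion sentence names neither analyte nor route. Read literally, it could reach 14C-AC886, where a curve last measurable at the 240 h draw has 2^(-236/119) = 25.3% extrapolated. The natural reading is narrower: F uses only the two quizartinib AUCinf values, and Section 9.5.2.1 applies its note by treatment. It is also not spelled out whether the exclusion covers F from AUClast, and the all-subject F is foreseen rather than promised. Sections 9.5 and 9.5.2.2 leave such detail to the SAP, to be final before database lock. No direction or size of selection bias in F has been shown.

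**Conclusion.** The concern does not hold. Its central premise, that extrapolation error cancels in the ratio, fails in the case it fears most: the error in F is -6.0% there, against -0.2% when both curves end together with the same error. The 20% limit thus guards F against a real error, and it is stated in advance.

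On the plan's figures the limit should seldom act: extrapolation is below 1%, against a trigger that needs a half-life of about 215 h or a curve ending before about 170 h. If a subject were excluded, his AUCinf would still appear in the summaries that include such subjects. A count of 5 instead of 6 would cost precision but break no stated error rate, because the study claims no power and tests no hypothesis.

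This rests on three assumptions: 14C drug stays measurable to at least the 192 h draw in most subjects; slope errors are of the order of 20%; and 73 h is close to the terminal half-life. Section 2.1 calls 73 h an effective half-life and Section 4.2 a terminal one. A longer terminal half-life would raise extrapolation, but 20% would still need about 215 h with data to the end. The choice of primary set is a matter on which competent analysts differ, and the remaining details of wording are not expected to change the result.

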10.1.2. Compliance Statement, Ethics, and Regulatory Compliance

This study will be conducted in compliance with the protocol, the ethical principles that have their origin in the Declaration of Helsinki, the ICH consolidated Guideline E6 for Good Clinical Practice (GCP) (CPMP/ICH/135/95), and applicable regulatory requirement(s) including the following:

- US FDA GCP Regulations: Code of Federal Regulations (CFR) Title 21, parts 11, 50, 54, 56 and 312 as appropriate and/or;
- Other applicable local regulations.

In addition, the Investigator will inform the Sponsor in writing within 24 hours of any urgent safety measures taken by the Investigator to protect the study subjects against any immediate hazard, and of any suspected/actual serious GCP non-compliance of which the Investigator becomes aware.

10.1.3. Administration of Radiation

Administration will be conducted in accordance with PPD [REDACTED] current PPD [REDACTED] license and Quotient Sciences' current ARSAC Employer license. Additionally a research application will be submitted to ARSAC to obtain approval for the conduct of the study before dosing.

The protocol will be reviewed and the final version will be approved by the ARSAC practitioner, PPD [REDACTED]

10.1.4. Supply of New Information Affecting the Conduct of the Study

When new information becomes available that may adversely affect the safety of subjects or the conduct of the study, the Sponsor will inform all Investigators involved in the clinical study, the EC, and regulatory authorities of such information, and when needed, will amend the protocol and/or subject information.

The Investigator should immediately inform the subject whenever new information becomes available that may be relevant to the subject's consent or may influence the subject's willingness to continue participation in the study. The communication should be documented on medical records, for example, and it should be confirmed whether the subject is willing to remain in the study.

If the subject information is revised, it must be re-approved by the EC. The Investigator should obtain written informed consent to continue participation with the revised written information even if subjects were already informed of the relevant information. The Investigator or other responsible personnel who provided explanations and the subject should sign and date the revised ICF.

10.1.5. Informed Consent

In obtaining and documenting informed consent, the Investigator should comply with the applicable regulatory requirements, and should adhere to GCP and to the ethical principles that have their origin in the Declaration of Helsinki. The ICF and any revision(s) should be approved by the EC prior to being provided to potential subjects.

The subject's written informed consent should be documented in the subject's medical records. The ICF should be signed and personally dated by the subject and by the person who conducted the informed consent discussion (not necessarily the Investigator). The original signed ICF should be retained in accordance with institutional policy, and a copy of the signed ICF should

be provided to the subject. The date and time (if applicable) that informed consent was given must be recorded.

If the subject cannot read, then according to ICH GCP Guideline, Section 4.8.9, an impartial witness should be present during the entire informed consent discussion. This witness should sign the ICF after the subject has consented to their participation. By signing the ICF, the witness attests that the information in the ICF and any other written information was adequately explained to and apparently understood by the subject and that informed consent was freely given by the subject.

A separate special consent for inherited genetic analysis will be obtained from subjects in accordance with health authorities in their particular region/country.

10.1.6. Subject Confidentiality

The Investigators and the Sponsor will preserve the confidentiality of all subjects taking part in the study, in accordance with GCP and local regulations.

The Investigator must ensure that the subject's anonymity is maintained. On the eCRFs or other documents submitted to the Sponsor, subjects should be identified by a unique subject identification as designated by the Sponsor. Documents that are not for submission to the Sponsor (e.g., signed ICF) should be kept in strict confidence by the Investigator.

In compliance with ICH GCP Guidelines, it is required that the Investigator and institution permit authorized representatives of the company, of the regulatory agency(s), and the independent EC direct access to review the subject's original medical records for verification of study-related procedures and data. The Investigator is obligated to inform the subject that his/her study-related records will be reviewed by the above named representatives without violating the confidentiality of the subject.

10.1.7. Data Integrity and Quality Assurance

10.1.7.1. Monitoring and Inspections

The Sponsor monitor and regulatory authority inspectors are responsible for contacting and visiting the Investigator for the purpose of inspecting the facilities and, upon request, inspecting the various records of the study (e.g., eCRFs, source data, and other pertinent documents).

The verification of adherence to the protocol; completeness, accuracy, and consistency of the data; and adherence to ICH GCP and local regulations on the conduct of clinical research will be accomplished through a combination of onsite visits by the monitor and review of study data remotely. The frequency of the monitoring visit will vary based on the activity at the study site. The monitor is responsible for inspecting the eCRFs and ensuring completeness of the study essential documents. The monitor should have access to subject medical records and other study-related records needed to verify the entries on the eCRFs. Detailed information is provided in the monitoring plan.

The monitor will communicate deviations from the protocol, SOPs, GCP, and applicable regulations to the Investigator and will ensure that appropriate action (s) designed to prevent recurrence of the detected deviations is taken and documented.

The Investigator agrees to cooperate with the monitor to ensure that any problems detected in the course of these monitoring visits are addressed to the satisfaction of the Sponsor and documented.

In accordance with ICH GCP and the Sponsor's audit plans, this study may be selected for audit by representatives from the Sponsor. Audit of study site facilities (e.g., pharmacy, drug storage areas, laboratories) and review of study related records will occur in order to evaluate the study conduct and compliance with the protocol, ICH GCP, and applicable regulatory requirements. The Investigator should respond to audit findings.

In the event that a regulatory authority informs the Investigator that it intends to conduct an inspection, the Sponsor shall be notified immediately.

10.1.7.2. Data Collection

An eCRF must be completed for each enrolled subject. Screen failure information will be collected at the clinical site in a log. All data collected for enrolled subjects during the study will be recorded in the individual, subject-specific eCRF. Instructions will be provided for the completion of the eCRF and any corrections made will be automatically documented via an "audit trail."

The eCRF should be kept current to enable the study monitor to review the subject's status throughout the course of the study. Upon completion of the subject's eCRF, it will be reviewed and signed off by the Investigator via the electronic data capture (EDC) system's electronic signature. This signature will indicate that the Investigator inspected or reviewed the data in the subject-specific eCRF, the data queries, and the site notifications and agrees with the eCRF content.

10.1.7.3. Data Management

Each subject will be identified in the database by a unique subject identifier **PPD**

To ensure the quality of clinical data across all subjects, a data management review will be performed on subject data according to specifications developed by the Sponsor. These processes will be performed according to the Data Management Plan.

Data will be vetted both electronically by programmed data rules within the application and manually. Queries generated by rules and raised by reviewers will be generated within the EDC application. During this review, subject data will be checked for consistency, completeness and any apparent discrepancies.

Data received from external sources such as central laboratories will be reconciled to the clinical database.

All AEs and Medical Histories will be coded using MedDRA (Version 23.1 or a more recent version). Medications will be coded using the World Health Organization (WHO) Drug Dictionary Global Drug Reference (Sep 2020 or a more recent version). Serious adverse events in the clinical database will be reconciled with the safety database.

10.1.7.4. Study Documentation and Storage

The Investigator will maintain a signature list of appropriately qualified persons to whom he/she has delegated study duties. All persons authorized to obtain informed consent and make entries and/or corrections on eCRFs will be included on the signature list.

Investigators will maintain a confidential screening log of all potential study candidates that includes limited information of the subjects, date and outcome of the screening process.

Investigators will maintain a confidential subject identification code list. This confidential list of names of all subjects allocated to study numbers on enrolling in the study allows the Investigator to reveal the identity of any subject when necessary.

Source documents are original documents, data, and records from which the subject's eCRF data are obtained. These include but are not limited to hospital records, clinical and office charts, laboratory and pharmacy records, diaries, microfiches, X-rays, and correspondence.

Electronic CRF entries may be considered source data if the eCRF is the site of the original recording (i.e., there is no other written or electronic record of data). In this study, the study eCRF may be used as source documents.

Records of subjects, source documents, monitoring visit logs, data correction forms, eCRFs, inventory of study drug, regulatory documents (e.g., protocol and amendments, EC correspondence and approvals, approved and signed ICFs, Investigator's agreement, clinical supplies receipts, distribution, and return records), and other Sponsor correspondence pertaining to the study must be kept in appropriate study files at the study site (site specific Trial Master File). Source documents include all recordings and observations or notations of clinical activities and all reports and records necessary for the evaluation and reconstruction of the clinical study. These records will be retained in a secure file for the period required by local laws or regulations or study site policy. Prior to transfer or destruction of these records, the Sponsor must be notified in writing and be given the opportunity to provide further instruction.

